## Table 11 Criteria for Clinically Notable Vital Signs

#### 8.7 Pregnancies

Results of local (urine or serum) and central (serum) pregnancy tests will be listed for all subjects enrolled in the study by treatment group. As it's expected for pregnancy counts to be small narratives will be provided in CSR.

93 Version: 1.0 Status: Approved Approved Date: PTK0796-AP-17202 Statistical Analysis Plan

Omadacycline (PTK 0796)

Paratek Pharma, LLC

PTK0796-AP-17202 Statistical Analysis Plan

## 9 CHANGES FROM PROTOCOL

Table 12 outlines protocol deviations together with justification for change.

## Table 12 Protocol Deviations and Justification for Change

	Protocol wording:	SAP language	Justification:
Micro-ITT pop primary	Bayesian analyses will be conducted after efficacy data (overall response at PTE) are available for approximately 40, 80 and 100 subjects in the micro-ITT population	Bayesian analyses will be conducted after efficacy data (overall response at PTE) are available for approximately 40, 80 and 100 subjects in the ITT population	Dose re-allocation criteria at the interims is not based on efficacy. Review is based on the safety and tolerability of the enrolled subjects (ITT).
Interim analyses for efficacy	Protocol sections: 5.1.1, 7.5, 7.8, 7.10, 12.2, 12.5.1, and 12.7	Protocol states that Bayesian analysis will be utilized in Interim Analysis decisions to alter sample size, randomization allocation, and/or stopping arm for efficacy or futility.	Due to low probability of success of dose differentiation with 40, 80, and 100 subjects efficacy stopping rules were not defined, see Table X2 DMC recommendations at Interim Analyses will be based on safety and tolerability. See Table 13 for details.
Presentation of Efficacy Endpoints	Protocol classifies efficacy endpoints as primary and secondary.	All efficacy endpoints of the study will be considered exploratory and are presented in this as in order of clinical importance.	In accordance with Administrative Memo dated 5/20/2019 all efficacy endpoints of the study will be considered exploratory to understand the performance of omadacycline in the treatment of acute pyelonephritis and to inform dose selection for a potential Phase 3 program.

## Table 13Probability of Successful Non-Inferiority Differentiation of OMC Groups and
LEV and Type 1 Error at Interim Analyses

Null hypothesized rates for OMC and LEV are 75%, Alternative hypothesizes rates OMC=65% LEV=75% Non-inferiority margin is assumed 10%					
# of subjects/group	Type I error when OMC rate is 62.5% and LEV=75%	Probability of success	Type I error		
10	4.4%	12.1%	4.4%		
20	3.0%	12.1%	3.0%		
30	2.8%	15.6%	2.8%		
40	2.8%	18.9%	2.8%		

OMC - omadacycline, LEV - levofloxacin

93 Version: 1.0 Status: Approved Approved Date: PTK0796-AP-17202 Statistical Analysis Plan

Omadacycline (PTK 0796)

Paratek Pharma, LLC

PTK0796-AP-17202 Statistical Analysis Plan

Table 14 illustrates probabilities of discontinuation at the analysis when data from 200 subjects is available for evaluation for various response rate scenarios.

Power column indicates power of successful detecting non-inferiority at 10% of OMC versus LEV with additional enrollment of 50 subjects per arm beyond total of 200.

#### Table 14Probabilities of Discontinuation

Additional enr	Additional enrollment 50/arm subjects enrolled					
			Probability of any OMC group discontinuation			
levofloxacin	OMC High dose	Pooled Groups 2-4	at 200 subject analysis	Pooled Groups 2-4	OMC High dose	Power*
0.75	0.75	0.75	0.0154	0.88074	0.10388	0.5695
0.75	0.75	0.625	0.1003	0.16462	0.73509	0.4377
0.75	0.625	0.625	0.7025	0.16567	0.13181	0.0298

The calculations were based on frequentist approach

\*Non-inferiority is based on lower limit of 95% confidence interval for difference in success rate to exceed -10%

OMC - omadacycline LEV - levofloxacin

TP-0293Version: 1.0Status: ApprovedApproved Date:PTK0796-AP-17202Statistical Analysis Plan

PTK0796-AP-17202 Statistical Analysis Plan

# APPENDIX 1 CLINICAL LABORATORY TESTS (CENTRAL) AND LOCAL URINALYSIS

#### Hematology:

- Hematocrit (Hct)
- Hemoglobin (Hgb)
- Mean corpuscular hemoglobin (MCH)
- Mean corpuscular hemoglobin concentration (MCHC)
- Mean corpuscular volume (MCV)
- Platelet count
- Red blood cell (RBC) count
- White blood cell (WBC) count with differential
- Coagulation (Ratio of prothrombin time (PT) and international normalized ratio (INR))

#### Pregnancy (all female subjects):

 Serum β-human chorionic gonadotropin (β-HCG)

#### Serum Chemistry:

- Alkaline phosphatase (ALP)
- Alanine aminotransferase (ALT)
- Aspartate aminotransferase (AST)
- Blood urea nitrogen (BUN)
- Calcium (Ca)
- Carbon dioxide (CO2)
- Chloride (Cl)
- Creatinine
- Creatine phosphokinase (CK)
- Gamma-glutamyl transpeptidase (GGT)
- Lipase
- Magnesium
- Phosphorus (P)
- Potassium (K)
- Sodium (Na)
- Total bilirubin

#### Urinalysis (Local Lab):

- Bilirubin
- Glucose
- Ketones
- Leukocyte esterase
- Microscopic examination of sediment with WBC count
- Nitrites
- Occult blood
- potential of hydrogen (pH)
- Protein
- Specific gravity
- Urobilinogen

## APPENDIX 2 DIRECTIONALITY OF WORST LABORATORY PARAMETERS

Laboratory Test	Parameter	Worst Value
Hematology	Hematocrit	Lowest value
	Hemoglobin	Lowest value

293Version: 1.0Status: ApprovedApproved Date:PTK0796-AP-17202Statistical Analysis Plan

## Omadacycline (PTK 0796)

Paratek Pharma, LLC

PTK0796-AP-17202 Statistical Analysis Plan

Laboratory Test	Parameter	Worst Value
	Red blood cell count	Lowest value
	Mean cell hemoglobin	Lowest value
	Mean cell hemoglobin concentration	Lowest value
	Mean cell volume	Lowest value
	White blood cell count	Lowest value
	Platelets	Lowest value
	Neutrophils	Lowest value
	Lymphocytes	Lowest value
	Monocytes	Lowest value
	Eosinophils	Highest value
	Basophils	Lowest value
Chemistry	Albumin	Lowest value
	Alkaline phosphatase	Highest value
	Alanine aminotransferase ALT/SGPT)	Highest value
	Amylase	Highest value
	Aspartate aminotransferase (AST/SGOT)	Highest value
	Urea	Highest value
	Bicarbonate	Lowest value
	Calcium	Both highest value and lowest value
	Cholesterol	Highest value
	Chloride	Both highest value and lowest value
	Creatinine	Highest value
	Creatine kinase (CK)	Highest value
	Gamma-glutamyl transpeptidase (GGT)	Highest value
	Blood glucose	Both highest value and lowest value
	Lactate dehydrogenase (LDH)	Highest value
	Lipase	Highest value
	Magnesium	Both highest value and lowest value
	Phosphate	Both highest value and lowest value
	Potassium	Both highest value and lowest value
	Sodium	Both highest value and lowest value
	Total bilirubin	Highest value
	Total protein	Lowest value
	Uric acid	Highest value
Coagulation	International normalized ratio (INR)	Highest value

293 Version: 1.0 Status: Approved Approved Date: PTK0796-AP-17202 Statistical Analysis Plan

Omadacycline (PTK 0796)

Paratek Pharma, LLC

PTK0796-AP-17202 Statistical Analysis Plan

## APPENDIX 3 MODIFIED DIVISION OF MICROBIOLOGY AND INFECTIOUS DISEASES ADULT TOXICITY TABLE

The DMID Adult Toxicity Table (21-Nov-2007) was modified to exclude the clinical component of the toxicity grading because clinical signs and symptoms related to abnormal laboratory values are not collected in this study. In addition, Grade 0 was added to the table so that shifts from normal could be analyzed. The grades for several parameters including enzymes were modified to ensure that any possible numeric value can be categorized appropriately (e.g., for creatinine, Grade 3 is defined as ">1.5-3.0×ULN" instead of "1.6-3.0×ULN").

For toxicity grades based on a multiple of the ULN, the normal range from the central laboratory will be applied.

For toxicity grades based on fixed values, the grades will be assigned regardless of the normal actual range values from the central laboratory. For example, a hemoglobin value of 10.0 gm/dL will be assigned a grade of 1 toxicity, even if the lower limit of normal from the laboratory was 9.8 gm/dL.

		HEMATO	LOGY		
	Grade 0	Grade 1	Grade 2	Grade 3	Grade 4
Hemoglobin (gm/dL)	> 10.5	9.5-10.5	8.0-9.4	6.5-7.9	< 6.5
Absolute Neutrophil Count (count/mm  )	> 1500	1000-1500	750-999	500-749	< 500
Platelets (count/mm  )	≥ 100,000	75,000-99,999	50,000-74,999	20,000-49,999	< 20,000
WBCs (count/mm  )	1000-10,999	11,000-12,999	13,000-14,999	15,000-30,000	> 30,000 or < 1,000
		COAGULA	ATION		
	Grade 0	Grade 1	Grade 2	Grade 3	Grade 4
Prothrombin time (PT) (sec)	≤1 x ULN	1.01-1.25 x ULN	1.26-1.5 x ULN	1.51 - 3.0 x ULN	> 3 x ULN
International normalized ratio (INR)	Increased	≤ULN	> 1 - 1.5 x ULN	> 1.5 - 2.5 x ULN	> 2.5 x ULN

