## 8.5 Clinical Laboratory Results

Clinical laboratory safety assessments include hematology (including coagulation), serum chemistry, and urinalysis.

Clinical laboratory parameters include those listed in the Appendix 1 Clinical Laboratory Tests (Central) and Local Urinalysis.

Baseline is defined as the central lab value closest to and prior to the first dose of test article. If no central lab value is available prior to the first dose of study drug, the local lab value that is closest to and prior to the first dose of study drug will be used as baseline. For by visit analyses, central lab values will be used unless no central lab value was obtained in the visit window. In this case, local lab values will be used for the by visit analyses. All lab values (central and local) are used for determination of the overall worst post-baseline value.

Laboratory data will be summarized by timepoint and for the overall worst post-baseline value using descriptive statistics (based on International System [SI] units) for the actual results and change from baseline for hematology and serum chemistry assessments.

Descriptive statistics (based on SI units) for chemistry, hematology and coagulation values and the change from baseline will be summarized by treatment group at each time point, and for the overall worst value post-baseline (which includes unscheduled visits).

Appendix 2 Directionality of Worst Laboratory Parameters provides the directionality of the worst values for each laboratory parameter.

Clinically notable laboratory values will be determined based on the Appendix 3 Modified Division of Microbiology and Infectious Diseases Adult Toxicity Table(DMID) criteria.

Shift tables will be presented to show the number of subjects with a laboratory value with a grade of 0, 1, 2, 3 or 4 at baseline versus the value at each visit. Number and percentage of subjects with at least a 2-grade increase from baseline (based on DMID criteria) will be summarized by treatment arm. Percentages for each laboratory test will be based on the number of subjects with a baseline and post-baseline evaluation of the specific laboratory test. A listing

93 Version: 1.0 Status: Approved Approved Date: PTK0796-AP-17202 Statistical Analysis Plan

Omadacycline (PTK 0796)

Paratek Pharma, LLC

PTK0796-AP-17202 Statistical Analysis Plan

will be provided for subjects who have at least a 2-grade increase from baseline in a given laboratory test.

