#### PTK0796-AP-17202 Statistical Analysis Plan

		CHEMISTRY			
	Grade 0	Grade 1	Grade 2	Grade 3	Grade 4
Hyponatremia (mEq/L) (Na)	> 135	130-135	123-129	116-122	< 116
Hypernatremia (mEq/L) (Na)	< 146	146-150	151-157	158-165	> 165
Hypokalemia (mEq/L) (K)	> 3.4	3.0-3.4	2.5-2.9	2.0-2.4	< 2.0
Hyperkalemia (mEq/L) (K)	< 5.6	5.6-6.0	6.1-6.5	6.6-7.0	> 7.0
Hypoglycemia (mg/dL) (glucose)	≥65	55-64	40-54	30-39	< 30
Hyperglycemia (mg/dL) (nonfasting and regardless of prior history of diabetes)  (glucose)	< 116	116-160	161-250	251-500	> 500
Hypocalcemia (mg/dL) (corrected for albumin)  (Ca)	> 8.4	8.4-7.8	7.7-7.0	6.9-6.1	< 6.1
Hypercalcemia (mg/dL) (correct for albumin)  (Ca)	≤ 10.5	10.6-11.5	11.6-12.5	12.6-13.5	> 13.5
Hypomagnesemia (mEq/L) (Magnesium)	> 1.4	1.4- 1.2	1.1-0.9	0.8-0.6	< 0.6
Hypophosphatemia (mg/dL) (P)	≥ 2.5	2.0-2.4	1.5-1.9	1.0-1.4	< 1.0
Hyperbilirubinemia (total bilirubin)	< 1.1×ULN	1.1-1.5×ULN	> 1.5-2.5×ULN	> 2.5-5×ULN	> 5×ULN
Urea	< 1.25×ULN	1.25-2.5×ULN	> 2.5-5×ULN	> 5-10×ULN	>10×ULN
Hyperuricemia (uric acid) (mg/dL)	< 7.5	7.5–10.0	10.1–12.0	12.1–15.0	> 15.0
Creatinine	$< 1.1 \times ULN$	1.1-1.5×ULN	> 1.5-3.0×ULN	> 3.0-6×ULN	> 6×ULN

 The DMID toxicity table reports hyperglycemia detected in nonfasting specimens obtained from subjects with no prior diabetes.

 Calcium corrected for albumin = [0.8 x (normal albumin - subject's albumin)] + serum Ca level

Where normal albumin = 4 g/dl, albumin is in g/dL and calcium is in mg/dL

	ENZYMES					
	Grade 0	Grade 1	Grade 2	Grade 3	Grade 4	
AST (SGOT)	< 1.25×ULN	1.25-2.5×ULN	> 2.5-5×ULN	> 5-10×ULN	>10×ULN	
ALT (SGPT)	< 1.25×ULN	1.25-2.5×ULN	> 2.5-5×ULN	> 5-10×ULN	>10×ULN	
GGT	< 1.25×ULN	1.25-2.5×ULN	> 2.5-5×ULN	> 5-10×ULN	>10×ULN	
Alkaline Phosphatase	< 1.25×ULN	1.25-2.5×ULN	> 2.5-5×ULN	> 5-10×ULN	>10×ULN	
Amylase	< 1.1×ULN	1.1-1.5×ULN	> 1.5-2.0×ULN	> 2.0-5.0×ULN	> 5.0×ULN	
Lipase	$< 1.1 \times ULN$	1.1-1.5×ULN	> 1.5-2.0×ULN	> 2.0-5.0×ULN	> 5.0×ULN	

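### SAP Appendix 3 leaves some prothrombin-time ratios without a toxicity grade, and its creatinine example contradicts its own table; the one-decimal rows need a unit and rounding rule, and the INR row needs checking

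*SAP*

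**What the plan says.** SAP Appendix 3 modifies a published adult toxicity table. On completeness it says "The grades for several parameters including enzymes were modified to ensure that any possible numeric value can be categorized appropriately", and on the added column, "Grade 0 was added to the table so that shifts from normal could be analyzed". Its creatinine illustration begins "for creatinine, Grade 3 is defined as" and then gives >1.5-3.0 × ULN.

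The bands at issue, as they read in the appendix:

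| Row | Grade 0 | Grade 1 | Grade 2 | Grade 3 | Grade 4 |
|---|---|---|---|---|---|
| PT (× ULN) | ≤1 | 1.01-1.25 | 1.26-1.5 | 1.51-3.0 | >3 |
| INR (as extracted) | *Increased* | ≤ULN | >1-1.5 × ULN | >1.5-2.5 × ULN | >2.5 × ULN |
| Creatinine (× ULN) | <1.1 | 1.1-1.5 | >1.5-3.0 | >3.0-6 | >6 |
| Low magnesium (mEq/L) | >1.4 | 1.4-1.2 | 1.1-0.9 | 0.8-0.6 | <0.6 |

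On the reference limit: "For toxicity grades based on a multiple of the ULN, the normal range from the central laboratory will be applied". Nothing is said about rounding the ratio or converting units before grading.

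SAP 8.5 uses the grades for clinically notable values, for Grade 0-4 shift tables, and for this count: "Number and percentage of subjects with at least a 2-grade increase from baseline (based on DMID criteria) will be summarized by treatment arm". A listing accompanies the count.

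**The concern.** A grading table has to assign exactly one grade to each result. If a result fits no band, the programmer must either leave it out of the shift table or choose a grade by an unwritten rule. If text and table give different grades for the same result, the 2-grade count depends on which one was programmed.

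Safety is a secondary objective of the trial, and these grade-based displays are part of the by-arm laboratory reporting. SAP 8.5 bases percentages on subjects with a baseline and a post-baseline evaluation of the test. A subject whose result was measured but not graded would therefore stay in the denominator without being able to count as an increase.

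**Working it through.** **1. PT gaps.** PT is graded as the ratio of the result to the central laboratory ULN, and that ratio is effectively continuous. Comparing the end of each band with the start of the next leaves three open gaps: 1 to 1.01, 1.25 to 1.26 and 1.5 to 1.51. From there to >3 the bands meet.

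To see which reportable results fall in the gaps, I assumed reporting to 0.1 s; the documents give neither the precision nor the ULN.

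| Assumed ULN (s) | Ungraded results (s), with ratio |
|---|---|
| 12.0 | 12.1 (1.008), 15.1 (1.258), 18.1 (1.508) |
| 12.5 | 12.6 (1.008), 15.7 (1.256), 18.8 (1.504) |
| 13.5 | 13.6 (1.007), 16.9 (1.252), 17.0 (1.259), 20.3 (1.504) |
| 14.5 | 14.6 (1.007), 18.2 (1.255), 21.8 (1.503) |

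At half-second steps of ULN from 11.0 to 16.0 s, each ULN has 3 to 5 ungraded values. If the ratio is first rounded to two decimals, the precision in which the bands are printed ("1.01-1.25 x ULN", for example), none remains.

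**2. Share of PT results affected.** Assume PT/ULN is normal with mean m and SD s. The ungraded share is the sum, over each ungraded value x, of Φ{[(x + 0.05)/ULN − m]/s} − Φ{[(x − 0.05)/ULN − m]/s}. For ULN 12.0 to 14.5 s:

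| m (s), × ULN | Results above ULN | Ungraded, of all results | Ungraded, of results above ULN |
|---|---|---|---|
| 0.92 (0.06) | about 8% | 1.6-1.9% | 20-23% |
| 0.97 (0.08) | about 34% | 3.1-3.7% | 9-11% |

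At least 99.6% of the ungraded share lies between 1.00 and 1.01 × ULN, the border of Grades 0 and 1. A post-baseline value there would be Grade 0 or 1 under any sensible rule, so it cannot be a 2-grade increase. A baseline value there leaves the change in grade undefined.

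**3. Creatinine.** Take a subject at 1.1-1.5 × ULN (Grade 1) who rises to 2 × ULN.
- By the table: Grade 1 to Grade 2, a rise of 1, not counted.
- By the text: Grade 1 to Grade 3, a rise of 2, counted and listed.

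A subject starting at Grade 0 is counted either way (a rise of 2 or 3).

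**4. One-decimal rows, with magnesium as the example.** The gaps are 1.1 to 1.2 and 0.8 to 0.9 mEq/L. Which results fall in them depends on how results are held:
- mEq/L to one decimal: none.
- mEq/L to two decimals: 0.81-0.89 and 1.11-1.19.
- mmol/L to two decimals (× 2): 0.41-0.44 and 0.56-0.59.
- mg/dL to one decimal (÷ 1.215): 1.0 (0.82 mEq/L) and 1.4 (1.15 mEq/L).

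Hemoglobin, potassium, calcium, phosphorus and uric acid have the same one-decimal pattern.

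**5. INR.** Read literally, ≤ULN is Grade 1, 1.2 × ULN is Grade 2, 1.8 × ULN is Grade 3, 3 × ULN is Grade 4, and nothing numeric is Grade 0. If *Increased* belongs to the row label, each grade drops by one and no Grade 4 band is left. The shift is uniform, so it cancels in any change from baseline: the 2-grade count is the same under both readings.

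**The case against.** The case for leaving this alone has several parts.

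- **Scope of the completeness statement.** It covers several parameters, not all. The enzyme, urea, bilirubin and creatinine rows are contiguous, as it says. A reader might infer that the SAP promises a grade for every laboratory value and breaks that promise; the text does not go so far. This stands. What remains is that PT is a ratio row with the kind of gap the appendix set out to remove, and that no rounding rule closes it.
- **INR.** A reader might infer that every normal INR will be reported as Grade 1 toxicity. The available text cannot establish that. The tables in this appendix show damage from PDF reading, and a label word displaced into the first cell would give the same five cells. The stated purpose of Grade 0 also points to ≤ULN being Grade 0. This stands, so the INR row is a point to check.
- **PT size.** The 9-23% figures use above-ULN results as the denominator and rest on assumed distributions. This stands, which is why the shares of all results are shown beside them. The role of PT is also uneven: SAP Appendix 1 lists it, but Protocol Table 3 does not, and SAP Appendix 2 names only INR under coagulation.
- **Magnesium.** SAP 8.5 ties SI units to descriptive statistics, not to grading, and no value is lost at one decimal in the table's own unit. This stands; the gap is conditional and not special to magnesium.
- **Creatinine.** The sentence is an illustration and the table is unambiguous. Applying the sentence would leave Grade 2 empty and collide with the printed Grade 3. The table is therefore very likely what is meant, but the contradiction is in an approved document and should be removed.

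**Conclusion.** Two defects hold on the documents. The PT bands leave three intervals of the ratio ungraded with no rounding rule, and the creatinine example contradicts the creatinine row. The one-decimal rows are a conditional weakness that depends on units and precision the SAP does not state. The INR row is unresolved until the source page is seen.

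The consequences are small. Under the assumed PT distributions about 2-4% of all PT results would be ungraded, nearly all at the Grade 0/1 border; the gaps themselves do not depend on those assumptions. The PT and one-decimal gaps give no grade rather than a wrong one. A reader might infer that abnormal results disappear from the safety reporting, but SAP 8.5 also provides descriptive statistics, worst values, transaminase and bilirubin thresholds, and listings of all results with high and low flags. Only the grade-based displays are exposed. They are descriptive, and no efficacy result depends on them. Severity: minor.

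**What to change.** - Write the PT bands as contiguous intervals: ≤1, >1-1.25, >1.25-1.5, >1.5-3.0 and >3 × ULN.
- For the one-decimal rows (magnesium, phosphorus and similar), either make the bands contiguous or state the unit and the rounding applied before grading.
- Change the creatinine example to Grade 2 so that it agrees with the table.
- Check the INR columns on the source page. Set them so that a normal INR is Grade 0, and say explicitly if the row has no Grade 4 band.

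The cost is table wording and grading code. No data collection changes, and it can be done before database lock.

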## 12.6 Secondary Endpoint(s)

### 12.6.1 Safety Endpoint(s)

All safety analyses will utilize the Safety population. Summary tables will be provided for all treatment-emergent adverse events (TEAEs). A TEAE is defined as an AE with a start date and time on or after the first dose of test article. Adverse events will be coded using the Medical Dictionary for Regulatory Activities (MedDRA) and will be summarized by presenting the number and percentage of subjects having each TEAE for each treatment group by system organ class (SOC) and preferred term (PT), by SOC, PT and severity, and by SOC, PT and relationship to test article. Additional tabulations will provide summaries by SOC and PT of subjects experiencing SAEs and TEAEs leading to discontinuation of test article.

The following variables will be analyzed descriptively by treatment group in the Safety population:

- Vital signs (systolic and diastolic BP, heart rate, body temperature), including change from Baseline by visit and time point measured
- Clinically notable vital signs (meeting predefined criteria as specified in the SAP) by visit and time point measured
- Laboratory parameters, including change from Baseline by visit and overall worst post-baseline
- Clinically notable laboratory parameters (meeting predefined criteria as specified in the SAP) by visit and overall worst post-baseline

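### SAP Appendix 3 grades calcium on an albumin that neither listed panel includes, and Appendices 2 and 3 treat white cell count in opposite directions, so some safety grades will be missing or wrong

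*SAP*

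**What the plan says.** SAP section 8.5 takes the direction of the worst laboratory value from Appendix 2 and the grades for clinically notable values from Appendix 3. Its shift tables compare the baseline grade with the grade at each visit. It also plans a summary and a listing of subjects whose grade rises by at least two, without saying whether that is judged visit by visit or on the worst value. Protocol 12.6.1 promises "Clinically notable laboratory parameters (meeting predefined criteria as specified in the SAP) by visit and overall worst post-baseline".

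**Calcium.** Both calcium rows in Appendix 3 are graded after albumin correction: "Calcium corrected for albumin = [0.8 x (normal albumin - subject's albumin)] + serum Ca level". Protocol Table 3 and SAP Appendix 1 list the same 16 serum chemistry tests. Calcium is among them and albumin is not. Protocol 8.7 does not name albumin among the tests expected from local laboratories. Appendix 2 nevertheless gives albumin a worst direction.

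**White cell count (WBC).** Appendix 2 reads "White blood cell count Lowest value". Appendix 3 has one WBC row. Grade 0 runs from 1,000 to 10,999/mm³, Grades 1 to 3 cover 11,000 to 30,000, and Grade 4 is "> 30,000 or < 1,000". On the meaning of Grade 0, the appendix says that "Grade 0 was added to the table so that shifts from normal could be analyzed".

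**Creatinine.** The introductory text of Appendix 3 says "for creatinine, Grade 3 is defined as" above 1.5 to 3.0 × ULN. The table in the same appendix puts that range in Grade 2.

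**The concern.** The three appendices do not fit together. The calcium grade needs an input that the listed panels do not supply, so a programmer would have to leave it missing or choose another rule without authority from the SAP.

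For WBC, the value labelled worst is the lowest, while nearly all of the grading is for high counts. One ordinal row also holds two opposite abnormalities, so a move from a high count to a very low one is measured as a small step along one scale.

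At stake are the clinically notable, shift and two-grade outputs for these two tests. Safety is a secondary objective, and SAP section 3.4 rests interim arm decisions mainly on safety and tolerability. The documents do not say whether the DMC uses these particular tables.

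**Working it through.** No planned figure has to be reproduced. I applied the Appendix 3 grades to illustrative values; none of them is trial data.

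**1. Calcium.** The formula is corrected calcium = measured + 0.8 × (4 − albumin), in mg/dL and g/dL. The documents give no albumin values, so I assume 2.5 to 5.0 g/dL. The correction then runs from 0.8 × 1.5 = +1.2 to 0.8 × (−1.0) = −0.8. The hypocalcemia bands are: above 8.4 Grade 0; 7.8–8.4 Grade 1; 7.0–7.7 Grade 2; 6.1–6.9 Grade 3. For a measured calcium of 7.6:

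| Albumin (assumed) | Corrected calcium | Hypocalcemia grade |
|---|---|---|
| 2.5 | 8.8 | 0 |
| 3.0 | 8.4 | 1 |
| 3.5 | 8.0 | 1 |
| 4.0 | 7.6 (no correction) | 2 |
| 4.5 | 7.2 | 2 |
| 5.0 | 6.8 | 3 |

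On the high side, Grade 0 is up to 10.5 and Grade 1 is 10.6–11.5. A measured 10.2 is Grade 0 uncorrected. At albumin 3.5 it becomes 10.2 + 0.4 = 10.6, which is Grade 1. Without albumin the specified grade is not determined.

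**2. WBC, overall worst value.** Appendix 2 takes the minimum:

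| Baseline (grade) | Post-baseline counts (grades) | Worst by Appendix 2 (grade) | Highest grade reached |
|---|---|---|---|
| 9,000 (0) | 32,000 then 7,000 (4, 0) | 7,000 (0) | 4 |
| 12,000 (1) | 16,000 then 6,000 (3, 0) | 6,000 (0) | 3 |
| 9,000 (0) | 14,000 then 8,000 (2, 0) | 8,000 (0) | 2 |

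A clinically notable flag taken from the worst value misses the high count in all three rows. Section 8.5 does not say which grade makes a value notable; the result holds for any threshold of Grade 1 or above.

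**3. WBC, two-grade rise.** Take a baseline of 16,000 (Grade 3) and a later count of 900 (Grade 4). The rise is 4 − 3 = 1, so the subject is not listed, whether the rule is applied by visit or to the lowest value. In the second row of the table above, the basis decides. By visit the rise is 3 − 1 = 2 and the subject is listed; on the worst value the grade goes from 1 to 0 and the subject is not.

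**4. WBC, low side.** Counts of 1,000, 1,500, 2,000, 3,000 and 4,000 are all Grade 0, and 999 is Grade 4. No intermediate low grade exists.

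**5. What still works.** Every whole-number WBC receives exactly one grade, and the by-visit shift tables do not use Appendix 2. Those tables can be produced as written.

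**6. Creatinine.** The table bands are 1.1–1.5, above 1.5–3.0, above 3.0–6 and above 6 × ULN for Grades 1 to 4. If the text were right, Grade 2 would have no range. Only the table can be programmed.

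**The case against.** The strongest case on the other side is that most of the laboratory reporting survives.

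- **By-visit tables.** A reader might infer that none of the WBC toxicity results can be produced. Section 8.5 does not support that: a count of 32,000 at a visit is graded 4 in that visit's shift table.
- **Leukopenia.** A reader might infer that low counts go unseen. They are ungraded from 1,000 up to the laboratory's lower limit, but the lowest WBC is summarised, values outside normal limits are flagged in the listings, and the neutrophil row has low-side Grades 1 to 4.
- **Baseline leukocytosis.** It is tempting to say that subjects enter with raised counts because they are infected. The inclusion criteria ask for pyuria or leukocyte esterase in urine, not a raised blood count, and no baseline WBC distribution is given. The frequency of the 16,000-to-900 pattern is therefore unknown.
- **Creatinine.** A reader might infer that the conflict changes who has a two-grade rise. The text is an illustration of how gaps between bands were closed, and the ordered table governs. It is a slip.
- **SAP precedence.** SAP section 1 says that the SAP prevails where the two documents differ. But section 8.5 does not withdraw the protocol's worst-value summary of notable laboratory results, and SAP Table 12 lists no such change.
- **Albumin.** Appendix 2 gives it a direction and local laboratory values are used, so it may be available for some subjects. The accurate statement is that albumin is not on the listed panels, not that it was never measured.

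These points narrow the concern. They do not remove the missing calcium input, the wrong direction for a WBC worst-value flag, or the two-direction WBC row.

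**Conclusion.** The rules are wrong as written on two tests, and the effect is confined to safety tables.

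For calcium, the specified grade cannot be obtained from the listed panels. Under the assumed albumin range, one measured value spans four grades.

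For WBC, a clinically notable flag on the overall worst value misses leukocytosis up to Grade 4. The two-grade summary and listing miss a fall from Grade 3 on the high side to Grade 4 on the low side.

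The WBC results follow directly from the two appendices. How many subjects would be affected cannot be estimated from the documents. The separate transaminase, bilirubin and Hy's law outputs in section 8.5 do not depend on any of this, and neither does efficacy.

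**What to change.** Before database lock:

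- **Appendix 2:** list both extremes as worst for WBC, as is already done for sodium, potassium and calcium.
- **Appendix 3, WBC:** split the row in two. The high row keeps the existing cut-offs. The low row keeps below 1,000 as Grade 4 and is otherwise Grade 0, unless the sponsor defines intermediate grades. Use the matching extreme for each row's worst-value, shift and two-grade outputs. Then 32,000 followed by 7,000 is Grade 4 on the high row, and 16,000 to 900 goes from Grade 0 to Grade 4 on the low row and is listed.
- **Section 8.5:** say whether the two-grade rise is judged by visit or on the worst value.
- **Appendix 3, calcium:** state that grading uses measured, uncorrected calcium unless albumin is available, and label the output accordingly.
- **Editorial:** make the creatinine example agree with the table. Glucose, uric acid and amylase also have grades and directions but are on neither panel; reconcile the three appendices at the same time.

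The cost is appendix wording and table programming. None of this needs new data; only adding albumin to the central panel would.
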